In-Home Technology for Caregivers of People With Dementia and Mild Cognitive Impairment: Spanish Language Homes

Unique Protocol ID: 1247267250000-2 Secondary IDs: 2SB1AG059458-04A1 Identifiers: NCT05159596

Document Date: July 12, 2023

Pre-Screening Procedures:

Spanish Language Homes caregivers may be recruited through caregiver organizations (e.g., Alzheimer's Association, clinics (e.g., Nebraska Healthcare), other locations where caregivers gather/visit (e.g., support groups, senior centers), and media (e.g., print, social, digital). We have created a flyer/email script for these organizations to use that describes the research study and introduces the in-home technology, as well as a physical flyer to be posted in physical locations caregivers are likely to frequent. All recruitment materials describe the general nature and goals of the research and provide information about what should be expected if they participate. The Berkeley research team is listed as the source for additional information and addressing questions in all materials.

Initial Encounter:

Interested caregivers will be directed to an online website to learn more about the study and complete a screening questionnaire to determine eligibility. Caregivers must 1) speak Spanish at home, 2) reside in the US and live with the person they are providing care for, 3) primarily use a smartphone (iPhone or Android), and 4) have WiFi internet service. Interested caregivers will also give their contact information for enrollment, as well as complete the consent to participate. Once a caregiver has been determined as eligible and enrolled through the website, a member of the Berkeley Psychophysiology Laboratory team will assess the capacity of the PWD to give consent to be in the study as a secondary subject. Once PWD consent is obtained either on their own, or through surrogate consent, caregiver participants will be sent a link to complete a set of questionnaires. Once PWD consent is obtained, People Power will mail the Presence Caregiver system to the caregivers for self-installation. People Power will be available to schedule virtual self-installation sessions if caregivers want by email or phone. Additional technical support for the system is available by email and phone during the course of the study.

Consent:

Participants will give consent online through the study website. Online consent requires participants to click on a box stating, "By clicking here, I indicate that I have read the above consent form and agree to take part in the research." Individuals receiving care (PWD) are asked to consent to participation as secondary subjects in order for information about them to be used for research purposes. In order to assess a patient's ability to consent to participation, a member of the research team will conduct a phone conversation with both caregiver and patient. The purpose of this conversation is to provide information about the study (e.g., participation responsibilities, compensation information, etc.) and to assess the PWDs cognitive capacity to consent for themselves using UCLA's "Decision-Making Capacity Assessment Tool." More specifically, a member of the Berkeley research team will determine the PWDs ability to 1) understand relevant study information, 2) ability to appreciate the situation and consequences of the study, 3) ability to rationalize or reason information presented, and 4) ability to make their own decision to participate in the study. If the investigator's evaluation is that the PWD can provide consent (i.e., the answer to questions 8 and 9 on the Assessment Tool are both "yes") the PWD will be asked to complete their own consent form via Qualtrics. If the PWD is judged to have diminished capacity (i.e., the answer to questions 8 or 9 are "no") then the caregiver will be asked to provide surrogate consent if the patient assents. Here, caregivers will be informed to the nature of their decision during the study including patient's participation and decision to participate in certain procedures for the patient in order to ensure that the caregiver will be willing to undertake these on-going responsibilities. In addition, caregivers will be asked to identify a witness who will be willing to provide a bystander signature when they are completing the Self-Certification of Surrogate Decision Maker Form.

Baseline Outcome Assessment:

Once consent procedures are complete, caregivers receive a Qualtrics link with their initial questionnaire. Identical Qualtrics questionnaires will be sent via email to caregivers in both research conditions at baseline, 3 months, and 6 months. The three sets of questionnaires will be identical, except the baseline questionnaire will also include a contact information form and "Information about person receiving care."

Randomization:

Sixty caregivers will be randomly assigned to the "active in-home technology" condition of the system and the remaining 60 caregivers will be assigned to the "control" condition. Randomization of participants in each group will be determined by People Power employees after the consent process.

Outcome Measures:

All caregivers-regardless of randomized study condition-complete questionnaires on three separate occasions during this study: baseline, 3-months, 6-months. The four outcome measures are: (a) Zarit Burden Interview-Short Form, a questionnaire measuring caregiver burden (Zarit, Reever, & Bach-Peterson, 1980). 12 items are rated on 0-4 scale. Range: 0-48. No subscales. Higher scores represent worse outcomes; (b) Center for Epidemiological Studies Depression Scale (CES-D), a questionnaire measuring depression (Radloff, 1977). 20 items are rated on a 0-3 scale and summed (range = 0-60). There are no subscales. Higher scores represent worse outcomes. The clinical cut-off is usually set at a score of 16; (c) Beck Anxiety Inventory (BAI), a questionnaire measuring anxiety (Beck, Epstein, Brown, & Steer, 1988). 20 items are rated on a 0-3 scale and summed (range= 0-60). Higher scores indicate worse outcomes. There are no subscales. A score greater than 36 is considered to be clinically significant; and (d) Satisfaction with Life Scale, a questionnaire measuring overall life satisfaction and well-being (Diener, Emmons, Larsen, & Griffin, 1985). 5 items scored on a 1-7 scale and summed (Range = 5-35). Lower scores indicate worse outcomes. A score of 20 is considered neutral with higher scores considered increasingly more satisfied and lower scores considered increasingly more dissatisfied.

Contact initiated by study staff

Caregivers receive \$75 for completing the installation of the system in their homes and \$25 for each questionnaire they complete (initial questionnaire, 3-months, and 6-months). Qualtrics questionnaires will be sent via email to caregivers in both research conditions at baseline, 3 months, and 6 months. After participation, a member of the research team will contact the caregivers to let them know they are welcome to uninstall and dispose of the system (or mail it back with costs covered), or they may choose to keep any sensors, devices, or equipment.

## **Statistical Analysis Plan**

## **Primary Outcomes**

All caregivers-regardless of randomized study condition-complete questionnaires on three separate occasions during this study: baseline, 3-months, 6-months. The four outcome measures include changes over the 6-month study period for the following scales: Zarit Burden Interview-Short Form, a questionnaire measuring caregiver burden (Zarit, Reever, & Bach-Peterson, 1980). 12 items are rated on 0-4 scale. Range: 0-48. No subscales. Higher scores represent worse outcomes; Center for Epidemiological Studies Depression Scale (CES-D), a questionnaire measuring depression (Radloff, 1977). 20 items are rated on a 0-3 scale and summed (range = 0-60). There are no subscales. Higher scores represent worse outcomes. The clinical cut-off is usually set at a score of 16; Beck Anxiety Inventory (BAI), a questionnaire measuring anxiety (Beck, Epstein, Brown, & Steer, 1988). 20 items are rated on a 0-3 scale and summed (range= 0-60). Higher scores indicate worse outcomes. There are no subscales. A score greater than 36 is considered to be clinically significant.; and Satisfaction with Life Scale, a questionnaire measuring overall life satisfaction and well-being (Diener, Emmons, Larsen, & Griffin, 1985). 5 items scored on a 1-7 scale and summed (Range = 5-35). Lower scores indicate worse outcomes. A score of 20 is considered neutral with higher scores considered increasingly more satisfied and lower scores considered increasingly more dissatisfied.

## **Statistical Methods**

Design: Caregivers will be randomized into two groups: Active In-Home Technology System and Limited In-Home Technology System. Subjects will be randomized 1:1. Randomization of participants in each group will be determined by People Power employees. Analyses of caregiver health and well-being will use 2 X 3 (Condition [active treatment vs control] X Time [time 1 vs time 2 vs time 3]) mixed model analysis of variance. In all analyses, significant main effects and interactions will be decomposed using a priori or post hoc comparisons depending on whether they are hypothesized or not. Bonferroni corrections will be used to control for Type I error resulting from multiple comparisons. Statistical Power. Tests of hypothesized Group differences (active treatment vs control condition) for caregiver health and well-being will have .80 power to detect a medium effect size (one-tailed, alpha = .05). Using repeated measures analysis of variance, tests of the interaction of Condition (2 groups) X Time (3 assessments) will have power of .99 to detect a medium effect size (correlation between repeated measures r = .5, alpha = .05).

Analysis: Descriptive statistics will be used to summarize all the clinical characteristics and demographic outcomes. These will be summarized overall, by treatment group, by assessment time, and by treatment group and time. Continuous variables will be summarized using means, standard deviations, and ranges. Categorical data will be summarized by number and percent. To evaluate the treatment effects, we will use repeated measures ANOVAs. The other predictors will be treatment group, and time (baseline, 3-months, and 6-months for caregiver outcomes). To evaluate treatment effects, an interaction term between treatment group and time will be included

to examine treatment group-related differences in the assessments for each outcome. Each significant interaction will be followed up with paired t-tests to examine treatment differences at each set of time points. Although this study involves 4 outcomes, we do not plan formal multiple comparison adjustments if the results fit a coherent pattern that is consistent with the context of similar studies. In this case, each result will reinforce the other, rather than detracting from one another, as required by formal multiple comparisons adjustments such as Bonferroni. Conversely, if only one or a very few measures reach statistical significance and their directions and/or magnitudes do not coherently fit with our a prior expectations, then we will note that the result(s) with p < 0.05 lack plausibility and could be due to chance, despite meeting the conventional cutoff for statistical significance.

Missing Data: If subjects either cannot or refuse to complete surveys we will use a sensitivity analysis approach in dealing with these missing data by performing analysis with 2 versions of scores: 1) with missing item interpolated using mean replacement by group, and 2) only using responses with 0% missing data. If the results differ for the two approaches, then we will report on the differences.

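### Baseline is analysed as a third outcome occasion and tested through a 2-df interaction, not used as a covariate; for 0.5 SD at 6 months this gives power of .68 to .81 instead of .88.

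*SAP*

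**What the plan says.** The SAP's Primary Outcomes section defines the endpoints as changes: "The four outcome measures include changes over the 6-month study period for the following scales". The protocol (Baseline Outcome Assessment) has every caregiver complete the scales three times: "Identical Qualtrics questionnaires will be sent via email to caregivers in both research conditions at baseline, 3 months, and 6 months". A baseline score on each outcome is therefore collected by design.

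The SAP's Statistical Methods then specifies "Condition [active treatment vs control] X Time [time 1 vs time 2 vs time 3]) mixed model analysis of variance". The Analysis paragraph confirms that baseline is a level of Time: "The other predictors will be treatment group, and time (baseline, 3-months, and 6-months for caregiver outcomes". Treatment is evaluated through the interaction: "To evaluate treatment effects, an interaction term between treatment group and time will be included". Two groups by three occasions give that interaction 2 degrees of freedom. A significant interaction is followed by paired t-tests, and significant main effects are also to be decomposed.

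Neither document mentions a baseline covariate, ANCOVA, or a model that constrains the arms to a common baseline mean. Neither names the between-arm difference at 6 months, with a confidence interval, as the main estimate.

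**The concern.** Baseline is measured before the intervention can act, so under randomisation the expected arm difference there is zero. Treating it as an outcome occasion has three consequences.

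- Any arm effect is estimated as a difference in raw change. This subtracts the whole baseline score instead of the part that predicts follow-up, and so adds noise.
- The test is an omnibus one. It asks whether the arms' profiles differ in any way over three occasions, while the stated outcome is change over 6 months.
- The Condition main effect, if used, averages in an occasion with no true difference and dilutes the effect.

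At stake are power in a trial of 120 caregivers, control of chance baseline imbalance, and a single interpretable effect estimate per outcome.

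**Working it through.** **Inputs**

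- n = 60 per arm: sixty caregivers go to the active condition and, in the protocol's Randomization section, "condition of the system and the remaining 60 caregivers will be assigned to the" control arm. The SAP agrees: "Subjects will be randomized 1:1".
- r = .5 between repeated measures and α = .05: SAP, Statistical Methods.
- Effect: the SAP says only that it is medium. I assume 0.5 SD at 6 months and 0 at baseline, with the month-3 difference ranging from 0 to 0.5 SD.
- Also assumed: two-sided tests, equal variances and correlations across occasions, and no dropout (range shown below).

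**The SAP's own power figures**

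- Interaction, stated power .99. With Cohen's f = .25, N = 120 and m = 3 occasions, λ = f²·N·m/(1−r) = .0625 × 120 × 3 / .5 = 45. On 2 and 236 df this gives power above .999, so the stated figure is met.
- Group difference: "will have .80 power to detect a medium effect size (one-tailed, alpha = .05". With d = 0.5, one-tailed power is .859 at 60 per arm and .799 at 50 per arm. The stated figure fits about 50 per arm, and no dropout allowance is given that would explain this.

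**Variance of the 6-month comparison, in units of SD²**

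- Raw change: 2(1−r) = 1.00
- Baseline-adjusted: 1−r² = .75
- Ratio .75. Since 1/.75 = 1.33, the saving equals a third more caregivers. The ratio is .65 at r = .3 and .85 at r = .7.

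**Power of the planned 2-df interaction**

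λ = (n/2)·Σ(d_t − d̄)²/(1−r), on 2 and 236 df.

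- Linear effect (0, .25, .5): Σ = .125; λ = 30 × .125/.5 = 7.5; power .682.
- Sustained effect (0, .5, .5): Σ = .1667; λ = 30 × .1667/.5 = 10; power .810.
- Late effect (0, 0, .5): λ = 10; power .810.

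Over all month-3 differences from 0 to 0.5 SD, power stays between .682 and .810.

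**Power of a single 6-month contrast**

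Noncentrality = 0.5/√(2v/60), where v is the variance above.

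- Raw change, v = 1.00: 2.739; power .775 (118 df).
- Baseline-adjusted, v = .75: 3.162; power .880 (117 df).

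Simulation with 20,000 trials per scenario gave .81 (late), .69 (linear) and .81 (sustained) for the interaction, and .876 to .881 for the adjusted contrast.

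**Matching the degrees of freedom**

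| Month-3 difference (SD) | 2-df interaction | 2-df baseline-adjusted joint test |
|---|---|---|
| 0 | .81 | .85 |
| .25 | .68 | .82 |
| .5 | .81 | .94 |

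**Sensitivity**

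| Scenario | Interaction | Raw change, 6 months | Adjusted, 6 months |
|---|---|---|---|
| r = .5, 60 per arm | .68–.81 | .775 | .880 |
| 10% dropout (54 per arm) | .63–.76 | .731 | .844 |
| 50 per arm | .60–.73 | .697 | .815 |
| 20% dropout (48 per arm) | .58–.71 | .679 | .799 |
| r = .3, 60 per arm | .53–.66 | .631 | .813 |
| r = .7, 60 per arm | .89–.96 | .939 | .967 |

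The dropout rates and the 50-per-arm row are illustrations; the documents give no dropout rate.

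**Condition main effect over three occasions**

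The mean of three scores has variance (1+2r)/3 = .667. The averaged difference is .25 SD (linear) or .333 SD (sustained), so the noncentrality is .25/√(2 × .667/60) = 1.677 or .333/√(2 × .667/60) = 2.236. Two-sided power is .38 or .60.

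**The case against.** The strongest reply is that nothing here is invalid. Under randomisation the interaction is an unbiased test of differential change, and change is what the SAP says it will study. That stands: the point concerns efficiency and the choice of estimate, not bias.

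Second, the gap from .68–.81 to .88 combines two changes, baseline adjustment and a focused 1-df contrast. That also stands, but adjustment gains on its own: from .775 to .880 at 1 df, and by 4 to 14 points at 2 df.

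Third, the SAP foresees a priori and post hoc comparisons, so it is not wholly unfocused. However, these decompose effects already found significant, and a paired t-test compares occasions within an arm. Neither supplies an ungated between-arm estimate at 6 months.

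Fourth, the SAP's group-difference test is one-tailed. On that basis the 6-month contrast has .859 (raw change) against .933 (adjusted); both exceed .80, and adjustment still wins.

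Fifth, the figures do not refute the SAP's .99. That figure rests on λ = 45, while a 0.5 SD difference at 6 months gives only 7.5 to 10. The two describe effects of very different size.

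Finally, the gain shrinks as r rises. At r = .7 it is about 1 to 8 points over the interaction and under 3 points over raw change. It does not reverse at any correlation examined.

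**Conclusion.** The concern holds. The plan uses an already collected baseline score in a less efficient way than it could, and it tests the treatment effect through an omnibus interaction. For 0.5 SD at 6 months, power is .68 to .81 as planned against .88 with a baseline-adjusted 6-month contrast; the part due to baseline handling alone is .775 against .88 at 1 df. These figures assume r = .5, 60 completers per arm, two-sided α = .05, equal variances and correlations, no true baseline difference, and a month-3 difference between 0 and 0.5 SD. The precision advantage is a large-sample result; the one degree of freedom spent on the covariate is negligible at this size. The change should be made, but the planned analysis would not be wrong without it.

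**What to change.** For each of the four outcomes, specify a mixed model with the 3- and 6-month scores as outcomes; fixed effects for arm, time, arm-by-time, baseline score and baseline-by-time; and an unstructured covariance across the two follow-up occasions. Name the arm difference at 6 months, with its 95% CI, as the main estimate, and the 3-month difference as secondary. Report both whether or not an interaction is significant.

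If the team prefers to keep baseline in the outcome vector, constrain the two arms to a common baseline mean. With complete data this serves the same purpose; with missing scores the two models can differ somewhat, so the SAP should name one. State that the Condition main effect over all three occasions will not be read as evidence of efficacy.

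The cost is SAP wording only. Baseline is already collected, and no visit, questionnaire or caregiver is added.

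### The SAP Bonferroni-corrects gated follow-ups without naming the family or divisor; if they are the three between-arm differences in change, the correction is redundant and costs about 5-11 points of power on the 6-month contrast under stated assumptions

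*SAP*

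**What the plan says.** The protocol's Randomization section fixes the size: "Sixty caregivers will be randomly assigned to the" active condition and "the remaining 60 caregivers will be assigned to the" control condition. Each caregiver answers four scales at baseline, 3 months and 6 months.

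The SAP's Statistical Methods section analyses each scale with a 2 x 3 "mixed model analysis of variance". On follow-up tests it says three things:

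- Under Design, "significant main effects and interactions will be decomposed using a priori or post hoc comparisons", according to whether they were hypothesized.
- The next sentence reads "Bonferroni corrections will be used to control for Type I error resulting from multiple comparisons". It gives no list of comparisons and no divisor.
- Under Analysis, "Each significant interaction will be followed up with paired t-tests to examine treatment differences at each set of time points".

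The SAP then says separately that no formal adjustment is planned across the four scales if the results are coherent. The Bonferroni sentence is therefore fairly read as governing follow-ups within one outcome. Adjustment across the four scales is a different matter and is not part of this point.

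**The concern.** Two layers of protection are stacked within an outcome: follow-ups run only if an omnibus test passes, and are then Bonferroni-corrected as well. With two arms and three visits, one natural set of follow-ups does not need the second layer, and applying it costs power. The contrast affected is the 6-month change, and the SAP defines its outcomes as change over the six months. A trial could also finish with a significant interaction and no pair of visits that passes.

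Because the family is not named, an analyst cannot tell whether alpha is to be divided by 3, by 6 or by something else, or whether the correction is needed at all. The answer depends on which comparisons are meant.

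**Working it through.** **Inputs from the documents.** 60 per arm (protocol, Randomization), 1:1 allocation, three visits, r = .5 between repeated measures, alpha = .05 (SAP, Statistical Methods).

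**Assumed.** The SAP says only that effects are medium. Conventional values are used: f = .25 for the interaction and d = .5 for an arm difference. The divisor is taken as 3. Outcomes are normal, SD 1, with equal correlations between visits.

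**1. The plan's own figures.** For the interaction, the noncentrality is f² x N x m / (1 - r) = .0625 x 120 x 3 / .5 = 45, on 2 and 236 df. Power is above .999, in line with the stated .99. For the group difference the SAP says the tests "will have .80 power to detect a medium effect size (one-tailed, alpha = .05"). At 60 per arm and d = .5 the one-sided power is .86; .80 corresponds to 50-51 per arm.

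**2. What f = .25 means at 6 months.** Let D be the arm difference at 6 months, with none at baseline.

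- Linear profile (0, D/2, D): f = D/√24, so D = .25 x √24 = 1.22 SD.
- Step profile (0, 0, D) or (0, D, D): f = D/√18, so D = .25 x √18 = 1.06 SD.

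With D = .5 the noncentrality is (.25/24) x 720 = 7.5 or (.25/18) x 720 = 10, where 720 = 120 x 3 / .5. The interaction test then has power of .68 or .81, not .99.

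**3. Why the gate is enough for one family.** Let d0, d3 and d6 be the active-minus-control differences at the three visits. The interaction null is d0 = d3 = d6. The three difference-in-change nulls are d0 = d3, d0 = d6 and d3 = d6.

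- If any two of these hold, the third holds too. That is the interaction null, which the gate tests at .05.
- Otherwise at most one holds, so at most one false rejection is possible, and it is tested at .05.

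By closed testing, each contrast can be tested at .05 after a significant interaction with family-wise error at most .05, provided the interaction test itself has level .05.

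**4. Power cost** (20,000 simulated trials per profile, 60 per arm). The entries are the chance of a significant interaction together with a significant baseline-to-6-month contrast.

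| r | Arm differences (SD) | Each at .05 | At .05/3 | Loss (points) |
|---|---|---|---|---|
| .5 | 0, .25, .5 | .663 | .609 | 5.5 |
| .5 | 0, 0, .5 | .730 | .622 | 10.7 |
| .5 | 0, .5, .5 | .731 | .620 | 11.1 |
| .7 | 0, .25, .5 | .888 | .857 | 3.1 |
| .7 | 0, 0, .5 | .926 | .861 | 6.5 |
| .7 | 0, .5, .5 | .927 | .866 | 6.1 |

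Losses were computed before rounding, and Monte Carlo error on power is about .3-.5 points. At the 1.06-1.22 SD effects from step 2 the loss is about 0. At r = .5 and D = .5, about 3.6% of trials have a significant interaction but no pair significant at .05/3; with .05 per contrast there are essentially none.

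**5. Family-wise error with the gate and no Bonferroni, by family.**

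| Follow-up family | Gate only | Gate plus Bonferroni |
|---|---|---|
| Three differences in change | .045-.052 | .015-.042 (/3) |
| Within-arm paired t-tests, only the active arm changing | .12-.17 | .02-.035 (/6) |
| Arm tests at each visit, effect only at 6 months | .08-.09 | about .03 (/3) |

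**6. The proviso on the gate.** The simulated gate is the uncorrected F under equal correlations. With correlations .7, .7 and .3 and no effect at all, gated error for the three contrasts without Bonferroni rises to about .06.

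**The case against.** The strongest reply is that the SAP does not name the three difference-in-change contrasts. The follow-ups it does name are paired t-tests. Taken literally these compare visits within an arm, up to six per outcome, and the wording could also mean arm comparisons at each visit. For both families the gate alone leaves error well above .05 (step 5), so Bonferroni does needed work there. The SAP also decomposes main effects. A Time effect can be significant without an interaction, and the interaction test does not protect its follow-ups. All of this stands.

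A reader might therefore infer too much: that the gate makes Bonferroni superfluous throughout, so that it can simply be deleted and several points of power recovered in any case. The documents do not support that. The redundancy holds for one family only, which the SAP neither adopts nor rules out.

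The power cost is also conditional. The SAP attaches no numerical effect to the 6-month contrast; d = .5 and the divisor of 3 are assumptions, and at the effect behind the stated .99 nothing is lost. Nor does the uncorrected F always hold its level, which is why the fix makes the gate robust.

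It can finally be said that Bonferroni after an omnibus test is valid and breaches no error rate. That is true, so this is a point about efficiency and specification. It remains worth acting on: difference-in-change contrasts are the ones that decompose a Condition x Time interaction, whereas within-arm paired tests do not compare treatments, and the family and divisor have to be stated anyway.

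**Conclusion.** The point holds in conditional form. The SAP corrects gated follow-ups by Bonferroni without stating the family or the divisor. If the follow-ups to the interaction are the three between-arm differences in change, a valid level-.05 interaction test already controls family-wise error within the outcome. Dividing by 3 then costs about 5-11 points of power on the 6-month contrast (60 per arm, r = .5, .5 SD at 6 months), 3-7 points at r = .7, and about nil at 1.06-1.22 SD. For within-arm paired tests, per-visit arm tests and main-effect follow-ups, an adjustment is still required.

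**What to change.** Replace the Bonferroni sentence with:

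> After a significant Condition x Time interaction for an outcome (tested with a Greenhouse-Geisser correction or an unstructured covariance), the three between-arm differences in change (3 months vs baseline, 6 months vs baseline, 6 vs 3 months) are each tested at two-sided .05 under closed testing. Any other follow-up comparisons within an outcome, including within-arm paired tests, per-visit tests and main-effect follow-ups, are adjusted by Holm instead of Bonferroni.

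The paired t-test sentence under Analysis should be aligned with this. Holm has the same family-wise error guarantee as Bonferroni and rejects at least as often, so the other families keep their protection.

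The cost is SAP wording only, with no new data or caregivers. The downside is that closed and Holm tests have no simple simultaneous confidence intervals, so the contrasts should be reported with ordinary 95% intervals labelled as unadjusted.

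### The SAP follows a significant Condition × Time interaction with paired t-tests, which measure change within an arm and cannot compare active with control

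*SAP*

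**What the plan says.** Five statements in the documents bear on this step.

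- **Allocation.** The Protocol (Randomization) assigns sixty caregivers to the active condition, and "the remaining 60 caregivers will be assigned to the" control condition. The SAP (Statistical Methods, Design) gives a 1:1 ratio. Neither document describes matching of caregivers across arms.
- **Treatment test.** The model is a 2 × 3 mixed analysis of variance, and the SAP (Analysis) says: "To evaluate treatment effects, an interaction term between treatment group and time will be included".
- **Follow-up test.** "Each significant interaction will be followed up with paired t-tests to examine treatment differences at each set of time points". This is the only sentence that names a test for the step after the interaction.
- **General provision.** The Design paragraph says "significant main effects and interactions will be decomposed using a priori or post hoc comparisons depending on whether they are hypothesized or not", and then "Bonferroni corrections will be used to control for Type I error resulting from multiple comparisons". The Statistical Power paragraph refers to "Tests of hypothesized Group differences (active treatment vs control condition") without giving a visit.
- **Descriptive output.** The clinical and demographic outcomes are tabulated without any condition on significance: "These will be summarized overall, by treatment group, by assessment time, and by treatment group and time".

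**The concern.** The follow-up sentence joins a test to a purpose that the test cannot serve. A paired t-test needs two measurements on the same unit. With independent arms the only available pair is one caregiver's scores at two visits, so the result describes change in that arm. A difference between treatments at 3 or 6 months is a contrast between different people, and no paired test estimates it.

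At stake is how a significant interaction is interpreted. The interaction says that the two arms follow different courses. It does not say at which visit they differ or by how much. The reader needs the active-minus-control difference at each visit with an interval, and the named test does not supply it. If both arms improve, the within-arm tests may all be significant in the same direction, which invites a reading of no difference just after the interaction has indicated one.

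**Working it through.** **Inputs from the documents.** 60 caregivers per arm; three assessments; correlation between repeated measures r = .5; alpha .05.

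**Assumptions, not in the documents.** Score SD = 1 in both arms; equal correlations; complete data; a true effect of 0.5 SD present at both 3 and 6 months; two-sided tests; paired tests run separately in each arm on all three visit pairs. The last item is one reading of the SAP sentence, which does not say whether tests are run by arm or how many pairs are meant.

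**1. The SAP's own figure.** The SAP gives the interaction a power of .99 for a medium effect. Taking medium as f = 0.25 (assumed), λ = N f² m/(1 − r) = 120 × 0.0625 × 3/0.5 = 45, with 2 and (120 − 2) × 2 = 236 df. Power exceeds 0.999, which agrees with .99. (With λ = N f² = 7.5 it would be about 0.68. That concerns the power statement and does not affect this point.)

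**2. What each procedure estimates.**

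- Paired test in one arm: t = (mean change)/(SD of change/√60), 59 df. It involves that arm only.
- Between-arm contrast: (active at visit − active at baseline) − (control at visit − control at baseline).

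The second quantity appears in no paired test. Pooling the arms before pairing would average the treatment difference away.

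**3. Precision of the contrast the plan does not name.** SE = √[2(1 − .5) × 2/60] = 0.183 SD. The 95% half-width is 0.183 × 1.970 = 0.36 SD. With Bonferroni correction over two visits (97.5%) it is 0.183 × 2.256 = 0.41 SD.

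**4. Why paired tests can look alike.** With r = .5 the SD of change is √[2(1 − .5)] = 1 SD. The chance that one arm's paired test is significant is therefore about 0.05, 0.48 and 0.97 for true changes of 0, 0.25 and 0.5 SD, and practically 1 for a change of 1 SD. If control improves 0.5 SD and active improves 1.0 SD, both arms are nearly always significant in the same direction.

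**5. The interaction under the assumed effect.** The arm differences over the three visits are 0, 0.5 and 0.5. Their squared deviations from the mean of 1/3 sum to 1/6. λ = (60/2) × (1/6)/(1 − .5) = 10, giving power of about 0.81.

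**6. Simulation.** 40,000 trials per control trend, keeping those with a significant interaction. Each paired result is coded as significantly down, significantly up or not significant. The arms give the same verdict when all three visit pairs agree.

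| Control trend | Same verdict on all pairs, unadjusted | Same, at .05/6 | Between-arm 6-month contrast significant at .05 |
|---|---|---|---|
| Stable | 0.1% | 1% | about 90% |
| Improves 0.25 SD | 20% | 5% | about 90% |
| Improves 0.5 SD | 84% | 73% | about 90% |
| Worsens 0.25 SD | 3% | 31% | about 90% |
| Worsens 0.5 SD | 0.1% | 1% | about 90% |

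The .05/6 column applies Bonferroni over three pairs in two arms. Its 31% reflects trials in which neither arm is significant on any pair. At .025 the between-arm contrast is significant in about 83%. A rerun with a new seed agreed within about one percentage point.

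**The case against.** The strongest reply is that this is a wording slip in a plan whose treatment test is sound. Much of that stands.

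- **A reader might infer that the trial has no valid test of treatment.** The documents do not support this. The interaction is a between-arm test, and the SAP names it as the means of evaluating treatment effects.
- **A reader might infer that between-arm comparisons are ruled out, or that an outcome with a non-significant interaction gets no estimate.** Neither follows. The Design paragraph foresees planned or post hoc comparisons with correction, and also decomposes significant main effects. Means and SDs by group and time are planned regardless of significance. What is missing is a between-arm contrast tied to a visit, with its test and interval.
- **A reader might infer that the sponsor will judge treatment by counting which arm reached significance.** The SAP states no such rule. The table shows what the paired tests would display, not a decision the plan prescribes. A conclusion of no difference would also require setting aside the significant interaction and the tabulated means.
- **The size depends on the control trend.** The documents give no expected trend. Control receives a limited version of the system, so some improvement is conceivable, but nothing supports 0.5 SD in particular. With control stable, the unadjusted paired tests almost always separate the arms.

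Charitable readings do not remove the error. If pairwise was meant, the named test is wrong. If simple effects of time within each arm were meant, the stated purpose is wrong. The general provision in the Design paragraph names no contrast and no visit, so it does not override the one sentence that names a test.

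**Conclusion.** The follow-up sentence is wrong as written and should be fixed; the primary treatment test is unaffected. Paired t-tests on these data measure change within an arm and cannot test or estimate active versus control. That conclusion rests on the design alone and needs no numerical assumption.

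The practical size does rest on assumptions. Under a sustained 0.5 SD effect and the other conditions listed, the chance that unadjusted paired results fail to separate the arms runs from negligible (control stable, or 3% or less if control worsens) to about 84% (control improves 0.5 SD). The 84% marks the unfavourable end of an assumed range and is not a forecast for this trial.

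**What to change.** Replace the follow-up sentence in the SAP (Statistical Methods, Analysis) with wording such as:

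> After a significant interaction, between-arm contrasts (active minus control difference in change from baseline) at 3 and at 6 months will be estimated from the same repeated-measures model and reported with confidence intervals. The Bonferroni correction described under Design will be applied across these contrasts. Within-arm paired changes are descriptive only.

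State the sidedness of these contrasts, because one-tailed testing appears only in the power statement for group differences. Use the interval level that matches the correction, and make the Design paragraph's provision for comparisons refer to these contrasts.

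Two additions are optional. A 3-to-6-month between-arm contrast belongs in the set if the sponsor meant to include that pair of visits. The contrasts and intervals could also be reported whether or not the interaction is significant.

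The cost is SAP wording only, with the same data and model. Under the assumptions above, correcting over two visits widens the half-width from about 0.36 to 0.41 SD and lowers the share of significant 6-month contrasts from about 90% to 83%, given a significant interaction. With a third contrast the half-width would be 0.183 × 2.411 = 0.44 SD.
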